#### **10.3.2.4.1      Exploratory Efficacy Analyses**

The analyses of the exploratory efficacy endpoints will be based on the ITT Analysis Set.

The total number of hospitalizations from the time of randomization through 30 days will be analyzed using a negative binomial regression model in a similar manner as described in [Section 10.3.2.3.1.1](#) for the number of hospitalizations through 90 days.

The exploratory time to event efficacy endpoints listed in 2 to 6 above, will be analyzed in a manner similar to that of the primary endpoint (see [Section 10.3.2.2.1](#)). Treatment comparison will be based on a covariate-adjusted Cox regression model for estimating the 1-sided Wald  $P$  value, the hazard ratio and its 2-sided 95% confidence interval. The effect over time will be illustrated with a plot of the complement  $(1 - KM)$  KM estimates. Event counts and percentages will be presented.

The analysis of the endpoint, total occurrence of rehospitalizations for CV events and all-cause death from the time of randomization through 90 days, will be based on the unmatched Win Ratio [[Pocock et al, 2012](#)], as described in [Section 10.3.2.3.1](#).

The exploratory endpoints including total occurrence of CV death, MI, and stroke from the time of randomization through 90, 180, and 365 days and total occurrence of all-cause death, MI, and stroke from the time of randomization through 90, 180, and 365 days will be analyzed using a negative binomial regression model in a similar manner as described in [Section 10.3.2.3.1.1](#) for the number of hospitalizations through 90 days.

The relationship between medical resource utilization and treatment with CSL112 will be explored and characterized using descriptive statistics. For the purpose of data analysis, the medical resource utilization endpoints including number of hospitalizations, length of stay and days in ICU or CCU will be treated as count data. For each subject, the following results will be derived across all hospitalizations occurring during the 90 days from randomization: total number of hospitalizations, total number of days hospitalized and the total number of

days spent in ICU or CCU. The analysis of these endpoints will be performed using a negative binomial regression model in a similar approach to that described for CV hospitalizations. Treatment comparisons will be based on the resulting incidence ratio, 95% confidence interval, and 1-sided  $P$  value obtained from the model.

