10.2 Analysis of Key Secondary Endpoints

The key secondary endpoints will be analyzed based on the ITT population. The null hypothesis associated with each key secondary endpoint will be tested at the time of final analysis. The analysis will be based on CEC-adjudicated events and an assessment of concordance between the investigator-reported and CEC adjudicated events will be undertaken. Multiplicity adjustments are discussed in [Section 7.4](#).

The three key secondary endpoints and their planned analyses are given below:

10.2.1 Total number of hospitalizations for coronary, cerebral, or peripheral ischemia through 90 days after randomization

A negative binomial regression model will be fitted to the count data arising from the number of hospitalizations. This analysis will consider only those hospitalizations adjudicated by the CEC as meeting endpoint criteria. The model will include fixed effects for treatment, region, index MI type, and index MI management, age (as a continuous variable), diabetes, peripheral artery disease, and history of MI, and a term for interaction between index MI type and index MI management which correspond to the covariates in the primary analysis. The log link function will be used and the log-transformed duration of follow-up (based on the date of last MACE ascertainment) within 90 days will be included in the model to account for the variable duration of follow-up across subjects. However, if the model fails to converge then the offset statement will be excluded. The mean rate of hospitalization per 90 days will

be presented by treatment arm. A 1-sided P value for treatment comparison, the rate ratio (CSL112: placebo) and its 95% CI will be estimated from the model.

A cumulative plot of recurrent hospitalization events will be generated using a non-parametric estimator for the mean cumulative function (MCF). Nelson [[Nelson, 2003](#)] introduced the MCF as a way to summarize the average number of events occurring in a subject by time t , within a population exposed to censoring events such as losses to follow-up and termination of the study. It assumes non-informative censoring and the risk set decreases only when an individual is removed from follow-up. A supportive data listing of hospitalization data will be produced.

The SAS code for fitting a negative binomial regression model to the count data from hospitalizations is given in [Appendix 15.5](#).

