The relationship between medical resource utilization and treatment with CSL112 will be descriptively summarized. The endpoints of medical resource utilization including the number of hospitalizations, length of hospital stay (days), CCU or ICU stay (days) and number of select surgeries/select procedures related to hospitalization for coronary, cerebral, or peripheral ischemia will be treated as count data for the purpose of analysis. For each subject, total counts either in number of admissions or duration of stay will be derived across all hospitalizations occurring during the 90 day period from randomization. The analyses of these endpoints will use a negative binomial regression model as described for the key secondary endpoint of CV hospitalizations described in [Section 10.2.1](#). Discharge to following CV hospitalization will be descriptively summarized with counts and percentages in each category by treatment arm.

The EQ-5D-3L is a patient self-assessment of five dimensions of health-related quality of life: mobility, self-care, usual activities, pain or discomfort and anxiety or depression. Each dimension is measured on a 3-point scale where a higher score corresponds to a worse health state. Scores from the individual dimensions will be used to calculate an overall utility score for each patient using the algorithm specified by the developers of the instrument [[EuroQoL, 2015](#)]. The EQ VAS is a continuous 100 point integer scale from 0 (the worst health you can imagine) to 100 (the best health you can imagine). Further details can be found in [Appendix 15.2](#).

Response to each of the five dimensions will be descriptively summarized. For each dimension and treatment, shift tables will be employed indicating the number of subjects whose response falls into a grid defined by the baseline value on one axis and the post-treatment value on the other axis. To compare treatments on each dimension, the number (%) of subjects with improvement, no change, or worsening from baseline to the post-treatment value will be analyzed using a chi-square test for a 2 x 3 contingency table with ordered categories of response.

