15.5 SAS Code

PROC FREQ (NEWCOMBE WILSON):

```
PROC FREQ DATA=<xxx>;
  TABLE treatment*<endpoint> / RISKDIFF (CL=(newcombe) column=2) OUT=<yyy>;
RUN;
```

Cox Proportional Hazards Regression Model:

PROC PHREG DATA=<xxx>;

```
CLASS TREATMENT MI_TYPE MI_MANAGEMENT REGION PERIPHERAL_ARTERY_DISEASE DIABETES MI_HISTORY;
MODEL <TIME>*<CENSORING>(1) = TREATMENT MI_TYPE MI_MANAGEMENT REGION AGE PERIPHERAL_ARTERY_DISEASE DIABETES
  MI_HISTORY MI_TYPE*MI_MANAGEMENT;
RUN;
```

Negative Binomial Regression Model using PROC GENMOD:

```
PROC GENMOD DATA=;
  Class TREATMENT MI_TYPE MI_MANAGEMENT REGION PERIPHERAL_ARTERY_DISEASE DIABETES MI_HISTORY;
  Model <endpoint> = TREATMENT MI_TYPE MI_MANAGEMENT REGION AGE PERIPHERAL_ARTERY_DISEASE DIABETES MI_HISTORY
    MI_TYPE*MI_MANAGEMENT/ link=log distbn=nb offset=logt;
  Run;
```

Imputation of Missing Baseline Covariates/Risk Factors:

```
PROC MI data= NIMPUTE=1 OUT=;
  CLASS PERIPHERAL_ARTERY_DISEASE DIABETES MI_HISTORY;
  VAR MI_TYPE MI_MANAGEMENT REGION AGE PERIPHERAL_ARTERY_DISEASE DIABETES MI_HISTORY;
  FCS LOGISTIC(PERIPHERAL_ARTERY_DISEASE DIABETES MI_HISTORY / LINK=GLOGIT);
RUN;
```

Tipping Point Analysis:

```
PROC PHREG DATA= ;
  CLASS MI_TYPE MI_MANAGEMENT REGION PERIPHERAL_ARTERY_DISEASE DIABETES MI_HISTORY;
  MODEL AVAL*NCNSR(1)= AGE MI_TYPE MI_MANAGEMENT REGION AGE PERIPHERAL_ARTERY_DISEASE DIABETES MI_HISTORY
    MI_TYPE*MI_MANAGEMENT;
  BAYES SEED=1234 PIECEWISE=HAZARD (INTERVAL=(10 30 50) PRIOR=GAMMA) NBI=2000 THINNING=50 NMC=2500;
  BY TRT;
RUN;
```

One-sided *P* value will be obtained as follows:

The Wald *P* value from the Cox/negative binomial regression model will be transformed to a 1-sided *P* values follows: if the estimated hazard/risk ratio for treatment effect is less than 1, the resulting *P* value will be set to 0.5*Wald *P* value; otherwise, if the estimated hazard/risk ratio is greater than 1 then the result *P* value will be set to 1-0.5*Wald *P* value.

Signature Page

CSL112_3001 - Statistical Analysis Plan - v4 - 11Jan2024

Signed By	Date (GMT)
PPD [REDACTED]	12-Jan-2024 16:00:01
Approved-Biostatistician Lead Approval	
PPD [REDACTED]	14-Jan-2024 20:07:11
Approved-Clinical Development Physician Approval	

Signature Page 1 of 1

--- Do Not Detach This Signature Page ---

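### Hospital days and CCU/ICU days are analysed with a model-based negative binomial standard error, so their 95% CIs may be too wide or too narrow; a robust standard error would settle it

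*SAP*

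**What the plan says.** SAP 10.4 lists length of hospital stay and CCU/ICU days through 90 days as exploratory endpoints 10b and 10c. With the other resource-use measures they "will be treated as count data for the purpose of analysis". On derivation it says: "For each subject, total counts either in number of admissions or duration of stay will be derived across all hospitalizations". The Protocol, section 10.3.2.4.1, likewise sums days per subject over all stays in the 90 days.

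The analysis is then the hospitalization-count model: "The analyses of these endpoints will use a negative binomial regression model as described for the key secondary endpoint of CV hospitalizations". That model (SAP 10.2.1) has a log link, and "the log-transformed duration of follow-up (based on the date of last MACE ascertainment) within 90 days will be included in the model". The only code given for it, in SAP 15.5, is a PROC GENMOD call whose model options are "link=log distbn=nb offset=logt". It has no REPEATED statement or other robust-variance option. For 180 and 365 days (additional endpoints 12b and 12c), SAP 10.4 again points to the approach of 10.2.1. No bootstrap, two-part model or other alternative is planned for the days endpoints.

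The Protocol states how the result is to be read: "Treatment comparisons will be based on the resulting incidence ratio, 95% confidence interval, and 1-sided" P value. SAP 10.4 calls P values for exploratory endpoints descriptive.

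**The concern.** A negative binomial model fits event counts such as admissions naturally. Hospital days are not separate events: one admission produces a block of days, and a subject without an admission has zero. The model has one dispersion parameter k, and it has to serve both the proportion of zeros and the spread among those admitted. When most subjects have zero, the likelihood sets k mainly to reproduce the zeros. The variance it then implies, mu + k·mu², is close to the true variance only if stay lengths happen to have the right spread.

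The estimated ratio of mean days is little affected. What is at stake is the standard error, and with it the 95% CI and 1-sided P value for four endpoints: hospital days and CCU/ICU days at 90 days, and the same two at 180 and 365 days. An interval that is too wide could obscure a saving in days; one that is too narrow could overstate it.

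**Working it through.** **Figures in the documents.** They state no admission rate, mean stay, SD, proportion of zeros, dispersion or CI width for these endpoints, so there is no planned figure to reproduce. The one design input used is 8700 subjects per arm. It agrees with the event target: 8700 × (0.064 + 0.0512) = 1002, against 1004 planned. All admission and stay inputs below are assumptions.

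**Formulas.** Let N be admissions per subject (mean λ, variance λ + d·λ²), S the length of a stay, and Y the summed days with mean mu.

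- True variance: Var(Y) = λ·Var(S) + Var(N)·E(S)², before any cap at 90 days.
- Negative binomial variance: mu + k·mu², with k from maximum likelihood.
- SE of the log ratio: sqrt[2·variance / (8700·mu²)].
- SE ratio: sqrt[(mu + k·mu²) / Var(Y)]. A value of 1 is correct, above 1 means the CI is too wide, and below 1 means it is too narrow.

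**Step 1: k follows the zeros.** Take two assumed mixtures of short and long stays, both with 0.15 admissions per subject and d = 1.

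| | Mixture A | Mixture B |
|---|---|---|
| Stays | 10% mean 30 days, 90% mean 3 | 25% mean 12 days, 75% mean 3 |
| Per-stay CV | 1.98 | 1.24 |
| Mean days per subject | 0.849 | 0.798 |
| Proportion with zero days | 0.870 | 0.869 |
| Fitted k | 21.1 | 20.1 |
| Zeros implied by k, (1 + k·mu)^(−1/k) | 0.870 | 0.868 |
| Model variance | 0.849 + 21.1 × 0.849² = 16.1 | 0.798 + 20.1 × 0.798² = 13.6 |
| SE ratio | 0.844 | 1.092 |
| True variance, model / ratio² | 22.5 | 11.4 |

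In both, the fitted k reproduces the zeros almost exactly. The zeros and means are similar, so the model variances are similar too, yet the true variances differ by a factor of about two. The CI is too narrow in A and too wide in B.

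**Step 2: the SE at trial size.** Assumptions: 8700 per arm, no treatment effect, 0.15 admissions per subject, d = 1, mean stay 5 days, log-normal stays, days capped at 90, log follow-up offset, 300 simulated trials per row.

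| Per-stay CV | Model SE | Monte Carlo SE | Sandwich SE | Model / sandwich | Coverage, model | Coverage, sandwich |
|---|---|---|---|---|---|---|
| 0.7 | 0.068 | 0.051 | 0.050 | 1.36 | 98.7% | 94.7% |
| 1.0 | 0.069 | 0.058 | 0.057 | 1.20 | 98.0% | 95.3% |
| 1.5 | 0.070 | 0.067 | 0.069 | 1.01 | 97.0% | 97.0% |
| 2.0 | 0.070 | 0.077 | 0.077 | 0.91 | 91.7% | 95.3% |

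The model SE barely moves while the true SE rises by half. With 300 trials, a coverage of 95% has a Monte Carlo SE of sqrt(0.95 × 0.05 / 300) = 1.3 points.

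Hand check at CV 0.7: Var(Y) = 0.15 × 3.5² + 0.1725 × 25 = 6.15, and SE = sqrt[2 × 6.15 / (8700 × 0.75²)] = 0.050. At CV 1.0 the same formula gives 0.057. Both match the sandwich column. At CV 1.5 and 2.0 it gives 0.072 and 0.089, above the simulated values, because it ignores the 90-day cap.

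On the ratio scale with a true ratio of 1, the typical 95% CI is exp(±1.96·SE). At CV 0.7 it is 0.87 to 1.14 (model) against 0.91 to 1.10 (sandwich). At CV 2.0 it is 0.87 to 1.15 (model) against 0.86 to 1.16 (sandwich).

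**Step 3: the range.** SE ratios over 0.05 to 0.30 admissions per subject, d from 0 to 3, mean stay 4 or 7 days, gamma or log-normal stays:

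| Per-stay CV | Model SE / true SE |
|---|---|
| 0.7 | 1.27 to 1.48 |
| 1.0 | 1.12 to 1.33 |
| 1.5 | 0.93 to 1.18 |
| 2.0 | 0.82 to 1.09 |
| Short/long mixtures, including ICU use in 30% of admissions (CV 1.2 to 2.6; 0.15 or 0.25 admissions) | 0.77 to 1.13 |

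A separate run with 0.10 to 0.25 admissions and mean stay 5 to 7 days gave 1.30 to 1.40 at CV 0.8, 1.11 to 1.20 at CV 1.2, 0.97 to 1.08 at CV 1.6 and 0.83 to 0.94 at CV 2.5.

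**The case against.** The strongest objection is that little depends on these intervals. The endpoints are exploratory, their P values are descriptive, they lie outside the gatekeeping scheme in SAP 7.4, and SAP 10.4 introduces resource utilization as a descriptive summary. That stands, and it limits the consequence to CI calibration. It does not remove the point, because the Protocol bases the treatment comparison on the ratio and its 95% CI, and a descriptive CI should still have its nominal coverage.

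A second objection is that the SAP nowhere calls days independent events, and that its model has a free dispersion parameter. That is also correct. The difficulty is that one parameter cannot match both the zeros and the spread of stays.

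A reader might go further and infer that the intervals are generally too wide, so that a real saving in days would be hidden. The documents do not support this. It requires stays of low variability, with a per-stay CV of about 1 or less in most settings. SAP 9.5 uses site-reported hospitalizations of all kinds, counts an extended index stay when it is due to a treatment-emergent serious adverse event, and merges overlapping stays at the longest duration. A mix of brief and long stays is therefore plausible, and with such a mix the CI is about right or too narrow.

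**Conclusion.** The concern holds as one of calibration, with no fixed direction. The plan applies a model-based negative binomial variance to summed days and has no safeguard if that variance is wrong. Under the stated assumptions the SE may be anywhere from about 23% too small to 48% too large. It is close to correct when the per-stay CV is near 1.5, and the nominal 95% CI covered between 91.7% and 98.7% in the trial-size simulations.

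These figures rest wholly on assumed admission rates and stay distributions. They were computed for 90-day totals. The mechanism carries over to 180 and 365 days, but its size there was not computed. The point estimates are little affected, and no primary, key secondary or stopping decision depends on these analyses.

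**What to change.** For length of stay and CCU/ICU days (endpoints 10b-c and 12b-c), keep the negative binomial point estimate. Take the SE, 95% CI and 1-sided P value from the empirical (sandwich) covariance by adding REPEATED SUBJECT=subject / TYPE=IND to the GENMOD call. Each subject contributes one record, so the statement serves only to request that covariance. Bootstrapping the ratio of mean days by subject is an acceptable alternative. State the choice in SAP 10.4 and show it in SAP 15.5.

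The cost is about one line of code and one sentence of text, with no new data. The resulting intervals may be wider or narrower than the model-based ones. In the trial-size simulations the sandwich interval covered 94.7% to 97.0%, whichever way the model-based error ran.

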Subjects will be randomized 1:1 to 1 of 2 treatment groups (CSL112 6 g or placebo). Randomization at baseline will be stratified by subjects' index MI type (STEMI vs NSTEMI), management of the index MI (PCI vs medically managed), and region (North America, Latin America, Western Europe, Central and Eastern Europe, or Asia Pacific). The study will consist of a Screening Period, an Active Treatment Period, and a Follow-up Period. Investigational product will be administered by intravenous (IV) infusion once weekly for 4 consecutive weeks. The primary efficacy outcome will be the composite of CV death, MI, or stroke from time of randomization through 90 days. Adverse event monitoring will continue through Visit 8 (Day 90), and all serious adverse events will be collected through the end of the study, regardless of relationship to investigational product. Subjects will be followed for occurrence of MACE for 365 days from randomization.

Synopsis Figure 1 Study Schema

EOS = End of Study; FMC = first medical contact.

**Primary Objective(s)** The primary objective of this study is to evaluate the efficacy of CSL112 on reducing the risk of MACE (CV death, MI, or stroke) from the time of randomization through 90 days in subjects with ACS (diagnosed with STEMI or NSTEMI).

**Primary Endpoint(s)** The primary endpoint is time to first occurrence of any component of the composite MACE, defined as CV death, MI, or stroke from the time of randomization through 90 days. The primary endpoint will include all MIs.

Key Secondary Objective(s)	
 
1. To evaluate the efficacy of CSL112 on reducing the total number of hospitalizations for coronary, cerebral, or peripheral ischemia.
 
2. To evaluate the efficacy of CSL112 on reducing the risk of MACE (CV death, MI, or stroke) through 180 and 365 days in subjects with ACS (diagnosed with STEMI or NSTEMI).
 

Key Secondary Endpoint(s)	
 
1. Total number of hospitalizations for coronary, cerebral, or peripheral ischemia from the time of randomization through 90 days.
 
2. Time to first occurrence of CV death, MI, or stroke from the time of randomization through 180 days.
 
3. Time to first occurrence of CV death, MI, or stroke from the time of randomization through 365 days.
 

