## **10           Statistics**

### **10.1 Sample Size**

#### **10.1.1       Estimation**

The study is designed as a superiority study. The sample size calculation is based upon the hypothesis that compared with placebo, CSL112 will have a 20% relative risk reduction (hazard ratio = 0.80) in the primary endpoint over 90 days of follow-up after randomization (ie, all subjects will be followed for a fixed duration of 90 days after randomization).

Assuming a 1-sided alpha of 0.025, not accounting for any dropouts from the study, and the interim analyses specified below, 1004 confirmed MACE (CV death, MI, or stroke) will provide at least 90% power. A 1-sided hypothesis test is necessary to differentiate directionality for interim analyses of futility and efficacy. Based on an assumed 90-day placebo event rate of 6.4%, an estimated 17,400 subjects (8700 per group) will be required.

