Following hospitalizations related to coronary, cerebral, or peripheral ischemia, counts of occurrences of discharge by category (to home with additional care, home without additional care, rehab, and skilled nursing facilities) will be summarized.

The EQ-5D-3L is a patient self-assessment of 5 dimensions of health-related quality of life: mobility, self-care, usual activities, pain or discomfort and anxiety or depression. Each dimension is measured on a 3-point scale where a higher score corresponds to a worse health state. Scores from the individual dimensions will be utilized to calculate an overall utility score for each patient using the algorithm specified by the developers of the instrument [EuroQol Group, 1990]. The EQ VAS is a continuous 100-point integer scale from 0 (the worst health you can imagine) to 100 (the best health you can imagine).

Response to each of the 5 dimensions will be descriptively summarized. For each treatment, shift tables will be employed indicating the number of subjects whose response falls into a grid defined by the baseline value on 1 axis and the post-treatment value on the other axis. To compare treatments on each dimension, the number (%) of subjects with improvement, no change, or worsening from baseline to the post-treatment value will be analyzed using a chi-square test for a 2 x 3 contingency table with ordered categories of response.

Both the utility score and the EQ VAS are continuous response variables describing the patient's self-assessment of their health status at baseline and post-treatment. Descriptive statistics including the mean, median, SD, minimum and maximum will be provided at baseline, post-treatment and for the change from baseline. The change from baseline will be compared between treatments employing an analysis of variance model including terms for treatment, index MI type, index MI management, region, an interaction term for index MI type by index MI management, age (as a continuous variable), diabetes, peripheral artery disease, and history of prior MI (excluding index MI).

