4.4 Randomization Procedures and Blinding

Subjects, who have provided written informed consent, completed the screening procedures and met entry criteria, will be randomized in a 1:1 ratio to CSL112 or placebo. The randomization schedule will be blocked and stratified by the type of index MI (STEMI or NSTEMI), whether the index MI is managed with PCI or medically managed, as well as region. The 5 levels of region include North America, Latin America, Western Europe, Central and Eastern Europe, and Asia Pacific. See [Appendix 15.3](#) for a list of regions, countries, anticipated recruitment rate for each region. Treatment assignment will occur within each of 20 strata with the goal of achieving treatment group balance at stratum level.

Treatment assignment to subjects will occur centrally, at the regional level, without regard to country or site. A web-based Interactive Response Technology (IRT) will be used to carry out the process of randomization.

The scope of the randomization schedule, including the fixed block size, will be specified by the CSLB study statistician or designee with the corresponding schedule generated by the IRT external service provider for the study. An initial dummy schedule will be reviewed and approved by the CSLB statistician or designee before the master list is generated using a different random seed. A dummy schedule will be used in programs for generating dry run tables, listings, and figures prior to database lock and study unblinding.

Blinding:

The study is designed to be double-blind with investigational site staff, subjects, and sponsor blinded to treatment assignment. Designated unblinded site personnel will be responsible for preparing the investigational product for infusion.

In order to ensure the integrity of blinded data, the investigator will not obtain a lipid panel during the active treatment period as the results may unblind treatment assignment.

The study will conclude at least 365 days after the last subject is randomized. Treatments will be formally unblinded only after database lock has been declared. However, if it becomes necessary to identify the treatment assignment for medical management of a study subject, in case of a medical emergency, the investigator may do so within the IRT system. The investigator is required to fully document the reason for unblinding in the source documents.

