7.2 Multicenter Studies

Treatment assignment is planned to be stratified by region including North America, Latin America, Western Europe, Central and Eastern Europe, and Asia Pacific. Sites will be grouped according to region. A summary table of recruitment by region, country, and site will be produced. Statistical analysis of efficacy endpoints will be adjusted for region.

Summary tables, figures, and listings will not be reported by investigator site nor will investigator site be a factor in any statistical models.

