10.4 Analysis of Exploratory Endpoints

The following set of exploratory endpoints is planned in this study. P values are intended to be descriptive. The analysis of the exploratory endpoint will be based on the ITT population.

1. Total number of hospitalizations for coronary, cerebral, or peripheral ischemia from the time of randomization through 30 days
2. Time-to-first occurrence of CV death, MI, or stroke or severe coronary ischemia requiring urgent revascularization from the time of randomization through 90 days
3. Time to first occurrence of CV death, MI, or stroke from the time of randomization through 30 and 60 days
4. Time to first occurrence of MI by type, according to universal definition, from the time of randomization through 90 days
5. Time to occurrence of CV death from the time of randomization through 365 days
6. Time to occurrence of non-CV death from the time of randomization through 365 days

7. Total occurrence of rehospitalization for CV events and all-cause death from the time of randomization through 90 days. Rehospitalization is defined as any site-reported post-index MI hospitalization (including extension of index MI hospitalization past randomization date due to a treatment-emergent serious adverse event) that is adjudicated, regardless of adjudication outcome, or a positively adjudicated triggered event linked to a site-reported adverse event. Urgent heart failure visits with a less than 24 hour stay are not considered.
8. Total occurrence of all-cause death, MI, and stroke from the time of randomization through 90, 180 and 365 days
9. Total occurrence of CV death, MI, and stroke from the time of randomization through 90, 180, and 365 days

10. Medical resource utilization from the time of randomization through 90 days:

- a. Number of total hospitalizations
- b. Length of hospital stay
- c. Number of cardiac care unit (CCU) or intensive care unit (ICU) days
- d. Select surgeries / select procedures related to hospitalization for coronary, cerebral, or peripheral ischemia (see [Section 9.5](#) for definition)
- e. Discharge to: home with additional care, home without additional care, rehabilitation or skilled nursing facilities following hospitalization for coronary, cerebral, or peripheral ischemia

11. Change in EQ-5D-3L data from baseline to day 90

The planned analyses of the exploratory efficacy endpoints are given below in the same order as the list of endpoints above.

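### The EQ-5D-3L dimension comparisons use no randomization factor, and the wording of the chi-square test leaves room for a version that does not use the ordering

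*SAP*

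**What the plan says.** The EQ-5D-3L is exploratory endpoint 11, "Change in EQ-5D-3L data from baseline to day 90" (SAP Section 10.4). That section counts it among the exploratory efficacy endpoints, as does Protocol Section 10.3.2.4.

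For each of the five dimensions, the numbers improved, unchanged and worsened are to be "analyzed using a chi-square test for a 2 x 3 contingency table with ordered categories of response". SAP Appendix 15.2 repeats the test, and Protocol Section 10.3.2.4.1 has the same wording: a "chi-square test for a 2 x 3 contingency table with ordered categories of response". None of the three places gives degrees of freedom, category scores, strata, covariates or an effect estimate. Appendix 15.5 contains no code for the test.

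Four other statements bear on this:

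- SAP Section 4.4: "Treatment assignment will occur within each of 20 strata", formed by two index MI types, two management types and five regions.
- SAP Section 7.2: "Statistical analysis of efficacy endpoints will be adjusted for region".
- SAP Section 10.4: the utility score and VAS are compared by an ANOVA that includes region, index MI type and index MI management, with further risk factors. Appendix 15.2 lists the three stratification factors only.
- SAP Section 10.4, on the exploratory endpoints as a group: "P values are intended to be descriptive".

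**The concern.** Two things are unsatisfactory, and they are separate.

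**Missing factors.** One questionnaire is analyzed in two ways. The utility score and VAS are adjusted for all three stratification factors, while the dimension comparisons are adjusted for none. The second choice also breaks the general rule in Section 7.2 as far as region is concerned.

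**Unfixed statistic.** A chi-square test on a 2 x 3 table usually means the Pearson test with 2 df, which gives the same answer whatever order the columns are in. The added words about ordered categories may instead point to a mean-score test with 1 df. Two programmers could follow the same sentence and produce different P values.

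If the 2-df version is run, power is lost against a shift in one direction. A small P value can also arise because improvement and worsening both rise, so it does not show which arm did better. It has no one-sided form either, although one-sided P values are planned for the time-to-event exploratory endpoints. No odds ratio or interval is planned for the dimensions that would supply direction and size.

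**Working it through.** **Plan's own figure.** The documents state no power, effect size, category rates or alpha for this test, so there is nothing to reproduce. The sample size used below is the stated one: "an estimated 17,400 subjects (8700 per group) will be required", allocated 1:1. It agrees with the event target: 1004 / 0.0576 = 17,431, where 5.76% is the pooled event rate in SAP Table 4-3.

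**Step 1. Cost of a second degree of freedom.** Power = P(noncentral chi-square with df and noncentrality λ exceeds the central 95% point). Two-sided alpha of 0.05 is an assumption. The critical values are 3.841 (1 df) and 5.991 (2 df). For a shift that the scores −1, 0, 1 capture fully, λ is the same for both tests.

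| λ | Power, 1 df | Power, 2 df |
|---|---|---|
| 7.849 | 80% | 70.9% |
| 10.507 | 90% | 83.5% |

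To regain 80% power the 2-df test needs λ = 9.635, and 9.635 / 7.849 = 1.23. For 90% it needs 12.654, and 12.654 / 10.507 = 1.20. The 2-df test therefore needs about 23% or 20% more patients.

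**Step 2. The same at this trial's size.** The category rates and odds ratios are assumptions. With placebo at 25 / 60 / 15% (improved / unchanged / worsened), a proportional-odds shift and 8700 per arm:

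| Odds ratio | λ, 1 df | λ, 2 df | Power, 1 df | Power, 2 df |
|---|---|---|---|---|
| 1.05 | 2.637 | 2.644 | 36.9% | 28.7% |
| 1.08 | 6.563 | 6.581 | 72.6% | 62.7% |
| 1.10 | 10.067 | 10.097 | 88.7% | 81.9% |
| 1.15 | 21.653 | 21.726 | 99.6% | 99.1% |

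The number of EQ-5D completers is not stated, so 7000 per arm was also tried, with two other sets of placebo rates (15 / 75 / 10% and 35 / 50 / 15%). Over all these cases the 1-df test gains 0.4 to 10.5 points.

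**Step 3. When the comparison reverses.** If improvement and worsening each rise by 1 point (25 / 60 / 15% against 26 / 58 / 16%) at 8700 per arm, the mean score is 0.25 − 0.15 = 0.10 in one arm and 0.26 − 0.16 = 0.10 in the other. The 1-df test sees no difference (power 5.0%), while the 2-df test has 68.5%.

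**Step 4. What the strata add.** The simulation used 20 strata, 6000 replicates and an odds ratio of 1.08. Regional shares came from SAP Table 15-2. Assumed shares were 50 / 50 for index MI type and 85 / 15 for PCI against medical management. The between-stratum SD of the log odds was varied.

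| SD between strata | 2 df, unstratified | 1 df, unstratified | 1 df, stratified |
|---|---|---|---|
| 0 | 62.3% | 72.4% | 72.5% |
| 0.2 | 62.3% | 71.5% | 72.0% |
| 0.4 | 61.1% | 71.6% | 73.0% |

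Stratification adds 0.1 to 1.4 points, with a simulation standard error of about 0.6 on each figure. Under no treatment effect, the rejection rates of the three tests lay between 0.047 and 0.058. The two highest, 0.057 unstratified and 0.058 stratified, came from the same scenario. There is no sign that leaving out the strata inflates the type I error.

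**The case against.** A reader might infer that the planned test ignores the ordering. The documents do not establish that. The sentence says the categories are ordered, and several ordered-category tests, including the row-mean-scores test recommended here, are chi-square tests. Nowhere do the documents say Pearson, unordered or 2 df. If a 1-df test was meant, the power loss in Steps 1 and 2 disappears and only the missing factors remain.

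A reader might also infer that this is the only efficacy analysis without the strata. It is not. The unmatched win ratio in Appendix 15.1 and the treatment-only Cox model in Section 10.1.1 also leave them out. The firm comparisons are with Section 7.2 and with the ANOVA for the same questionnaire.

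Three further points stand:

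- Direction is not lost from the report. The plan shows counts and percentages by category, shift tables by dimension and arm, and adjusted ANOVAs of the utility score and VAS.
- An ordinal test is not stronger against every alternative, as Step 3 shows. Moving to it is a choice about which effect to look for. The planned counts and shift tables would still show a rise in both improvement and worsening.
- The endpoint lies outside the gatekeeping procedure and no decision depends on it.

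These points limit the size of the concern. They do not explain why one part of the questionnaire is adjusted and another is not, or which statistic the programmer should compute.

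**Conclusion.** The point holds in a narrow form. The missing randomization factors are plain on either reading of the test, and they conflict with Section 7.2 for region. The practical cost is small: about 0 to 1.4 points of power under the assumed stratum effects, with no visible inflation of error. The gain is mainly consistency within the questionnaire.

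The larger figures, 80% falling to about 71% and 90% to about 84%, are conditional. They apply only if the 2-df test is run, the shift is in one direction and alpha is 0.05 two-sided. The wording permits that test but does not require it.

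The primary and key secondary analyses are unaffected. With descriptive P values on an exploratory endpoint, this is a low-priority improvement. A clear estimate with an interval would serve the reader better than an undirected P value.

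**What to change.** In SAP Section 10.4 and Appendix 15.2, replace the sentence on the dimension comparison with a named test: the Cochran-Mantel-Haenszel row-mean-scores statistic, 1 df, scores −1 / 0 / 1 for worsened / unchanged / improved, stratified by index MI type, index MI management and region. With these scores, the arm difference is the difference in percent improved minus percent worsened, so its sign shows the direction.

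Alongside it, report a common odds ratio with 95% CI from a proportional-odds model with treatment and the same three factors. Keep the counts and shift tables, because they show a rise in both improvement and worsening, to which the 1-df test is insensitive. Add the code to Appendix 15.5.

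The cost is a sentence in two places and a few lines of code, settled before unblinding. No new data, visits or patients are needed. Protocol Section 10.3.2.4.1 carries the same wording. If the named test is regarded as a change from it, record that in SAP Section 5, which at present lists no changes.
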